4.3.2. Safety of RLYB212 in the HPA-1a Positive Neonate

4.3.2.1. Type, Seriousness, and Incidence of AEs

The neonatal adverse events will be collected from the time of birth till 4 to 6 weeks of age. MedDRA version 27.0 or above will be used to code the AEs. All neonatal AEs will be graded according to neonatal adverse event severity scale (NAESS version 1.0 or higher).

The following summaries of neonates will be provided for NFAS (the number and percentage of participants) including but not limited to:

- All AEs (*).
- All AEs related to study treatment (*).
- All AE leading to worsening of a pre-existing condition (*).
- All AEs with outcome of death.
- All AEs with outcome of death, related to study treatment.
- AEs of NAESS grade 3 or higher.
- AEs of NAESS grade 3 or higher, related to treatment.
- All SAEs (*).
- All SAEs, related to study treatment.
- All SAE leading to worsening of a pre-existing condition (*).
- All SAEs with outcome of death.
- All SAEs with outcome of death, related to study treatment.

The incidences of above adverse events will also be summarized by the number of participants reporting at least one event, percentage of participants with the 95% exact Clopper-Pearson confidence interval for the percentage.

The selected summaries (marked above in *) will be presented by MedDRA System Organ Class (SOC) and Preferred Term (PT). Frequencies and percentages of participants reporting each preferred term will be presented (i.e., multiple events per participant will not be accounted for, except for event level summaries). All AEs, SAEs, all AEs with outcome of death, all SAEs with outcome of death, all AEs leading to study discontinuation, all SAEs leading to study discontinuation will be summarized for neonates. The selected summaries (marked in above) will be presented by MedDRA System Organ Class (SOC) and Preferred Term (PT).

All reported neonatal AEs will be listed along with date of onset, date of resolution (if AE is resolved), investigator's assessment of NAESS grading, relationship to study treatment, action taken and outcome, SAE status MDR and concomitant of additional treatment given to due to AE).

4.3.2.2. Newborn Physical Examination Findings, Including APGAR Score

Newborn physical examination findings (gender, birth weight, length, head circumference, APGAR score taken at 1 min and 5 min after birth) will be summarized for NFAS.

Newborn physical examination findings will be listed for NFAS, by newborn participant id.

4.3.2.3. Vital signs

All available vital signs collected from live births will be listed for NFAS, by newborn id and by visit.

4.3.3. Immunogenicity of RLYB212

To assess the immunogenicity of RLYB212, anti-drug antibody in serum will be evaluated as described in SoA. Serum samples should also be collected at the final visit from participants who discontinue study intervention or are withdrawn from the study.

Serum ADA findings will be summarized for IMAS, by study visits. The number and percentage of participants with both positive and negative ADA samples as well as the titers, persistence or transience of positive ADA samples will be summarized, and a by- participant listing will be presented for all immunogenicity assessments using the IMAS. Definition of common terms applied in the descriptions of immunogenicity are as below:

- Pre-existing ADA: refers to antibodies reactive with the biologic drug that are present in participants before treatment (or before initiation of the clinical study).
- Treatment-emergent ADA: ADA developed de novo (seroconversion) following biologic drug administration.
- Treatment-boosted ADA: Pre-existing ADA that were boosted to a higher level following biologic drug administration.
- Titer: a quasi-quantitative expression of the level of ADA in a sample; magnitude of the ADA response.
- Transient ADA: Treatment-induced ADA detected at sampling time points during the treatment (including follow-up period if any), where the first and last ADA-positive samples (irrespective of any negative samples in between) are separated by a period less than 16 weeks, and the participant's last sampling time point is ADA-negative.
- Persistent ADA: Treatment-induced ADA detected at two or more sampling time points during the treatment, where the first and last ADA-positive samples (irrespective of any negative samples in between) are separated by a period of 16 weeks or longer or treatment-induced ADA is detected in the last sampling time point.

ADA impact assessment

Individual serum RLYB212 concentration-time (hour) profiles following administration of RLYB212 SC by participant ID and ADA status shall be presented in a figure, on a semi-log scale. ADA positive vs. negative participants shall be highlighted in the figure for visual comparison.

The results will be listed for each participant by visit.

4.3.4. Pregnancy and Neonatal Outcomes

The following pregnancy and neonatal outcomes will be summarized by the frequency of participants with the specified outcome and percentage with 95% Clopper-Pearson exact confidence interval for the FAS.

- Number of spontaneous abortions.
- Number of elective abortions.
- Number of stillbirths.
- Number of premature births.
- Number of full-term births (≥ 37 completed weeks of gestation).

4.3.5. Overall Health and Development of Infants at 4-6 Weeks and 12 Months of Age

For NFAS, general health assessment of livebirths will be collected at birth, at 4- 6 weeks; and a developmental assessment will be conducted at 12 months of age. All available, health status will be summarized and listed. Any abnormality in the health assessment will be flagged in the listing.

The development assessment at 12-months will consist of the parent-reported ASQ-3 data. Raw questionnaire data will be centrally scored and analyzed according to published methods for the instrument (Ghimire, S., Ang, E., Deibert, M., Hartvich, E., & Fucile, S. (2024)).

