Screening Part 1 is an initial visit that includes the informed consent, demographic questioning (including obstetric history), and the collection of a blood sample for FNAIT testing (Table 1-2). This visit is to take place no earlier than GW 6. Individuals will consent to HPA-1 genotyping (Test 1) and, if HPA-1b/b, subsequent screening for HLA-DRB3*01:01 (Test 2), anti-HPA-1a antibodies (Test 3), and confirmation of fetal HPA-1a genotype (Test 4), as required.

Two distinct samples and analyses are performed, per industry practice, to confirm absence of the HPA-1b allele in the fetus, with timing between sampling ~2 weeks.

8.1.2 Screening Part 2

Participants who meet all eligibility criteria in Screening Part 1 (SoA, Table 1-3, ie, HPA-1b/b and HLA-DRB3*01:01 positive genotype; anti-HPA-1a alloantibody negative; fetal HPA-1a/b genotype) and who provide informed consent for Screening Part 2 (SoA, Table 1-3) will be assessed to determine if they meet all eligibility criteria to enter the antenatal treatment phase and to receive treatment with RLYB212 according to the protocol.

Dosing with RLYB212 will be initiated at Visit 3, which must occur no later than GW 16. That is, if the fetal HPA-1 genotype is pending and will not be available by the planned baseline visit at GW 16, the subject will be dosed with the initial dose of RLYB212 pending the result (of the

replicate tests), provided all other Screening Part 2 criteria are met. A second dose of RLYB212 will not be given if definitive fetal HPA-1a results are not available by Visit 4 (~GW 20). If the fetal HPA-1a genotype data become available after the initial dose of RLYB212 is given and the fetus is HPA-1b/b, ie, not at risk for HPA-1a alloimmunization, the participant will be discontinued from treatment, followed at a safety visit 4 weeks later and then discharged from the study to receive normal prenatal care and follow-up by their physician. In this case, the participant would have been determined not to be at risk for development of HPA-1a alloimmunization and FNAIT.

The study has been designed with multiple sequential cohorts ([Section 1.2.1](#)). Therefore, if a participant has been determined to be eligible for RLYB212, but the cohort has been fully enrolled, the participant will be requested to consent for the non-interventional (observational) sub-study.

Eligibility for the non-interventional (observational) sub-study is presented in [Table 1-1](#).

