9.4.3 Secondary Endpoints

RLYB212 exposure in the neonate will be evaluated by cord blood concentration of RLYB212, which will be a single measurement, and neonatal thrombocytopenia will likewise be evaluated by cord blood platelets.

Other aspects of safety of RLYB212 exposure in the neonate will be evaluated during the postpartum follow-up period in terms of type and seriousness and incidence of AEs, physical examination findings including APGAR scores, vital signs and cord blood levels for platelets, hematocrit, hemoglobin, reticulocytes, total bilirubin, and any additional safety testing done on the neonate on an ad hoc basis.

RLYB212 immunogenicity data and the presence of ADA, and whether there is a neutralizing response, will be determined.

Pregnancy and neonatal outcomes following antenatal RLYB212 administration will include:

- Number of spontaneous abortions, defined as non-deliberate fetal death which occurs prior to GW 19.
- Number of elective abortions, defined as deliberate termination of pregnancy at any time in gestation.
- Number of stillbirths, defined as non-deliberate fetal death anytime in gestation on or after GW 19.
- Number of premature births, defined as live birth prior to GW 37.
- Number of full term births (\geq GW 37).
- Overall health and development of infants at 4-6 weeks and 12 months of age.

- Neonatal thrombocytopenia and severe neonatal thrombocytopenia, as defined by a platelet count $< 150 \times 10^9/L$ and $< 50 \times 10^9/L$, respectively, collected as a part of the cord blood sample.

Maternal alloimmunization to HPA-1a will be determined by a measurement of maternal circulating anti-HPA antibodies at 10 weeks postpartum or 10 weeks from the date of the pregnancy-terminating event (ie, abortion [spontaneous/elective] or stillbirth).

Where possible, data will be summarized using descriptive statistics and listed.

9.4.4 *Tertiary/Exploratory Endpoints*

Not applicable.

9.4.5 *Other Safety Analyses*

All routine safety analyses will be performed on the Safety Analysis Set. Data will be presented separately for maternal participants and neonates/infants.

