2.1. Multiplicity Adjustment

No hypotheses are planned to be formally tested using inferential statistics in this study; hence multiplicity is not a concern.

3. Analysis Sets

For purposes of analysis, the following populations are defined:

Table 1: Analysis sets

Population	Description
Full Analysis Set (FAS)	All participants that fulfill the criteria for screening part 1 and part 2, and received one or more full doses of RLYB212.
Neonate Full Analysis Set (NFAS)	Neonates born to participants that fulfill the criteria for screening part 1 and part 2 and received one or more doses of RLYB212.
Safety Analysis Set (SAS)	All participants in the study who received any dose of RLYB212.
RLYB212 PK Analysis Set	All participants received at least one dose of RLYB212 and at least one RLYB212-PK sample has been analyzed will be included.
Immunogenicity Analysis Set (IMAS)	All participants that fulfill the criteria for screening part 1 and part 2, received one or more doses of RLYB212 and had detection and categorization of ADA.

Population	Description
Alloimmunization Analysis Set (AAS)	All participants who had at least one screening (Screening Part 1 or 2) or baseline (Visit 2) determination of anti-HPA-1a activity and a subsequent determination of anti-HPA-1a activity postpartum.

4. Statistical Analyses

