4.1.4.3. Analysis Sets

The number and percentage of participants in each analysis set and reasons for exclusions from each analysis set will be summarized for FAS. The participants included and excluded in each analysis set will be listed for FAS.

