4.5. Other Analyses

4.5.1. Extent of Exposure

Study drug exposure will be summarized for participants who received RLYB212 for the safety analysis set, for duration of exposure, number of doses, cumulative dose, and number of missed doses.

Duration of exposure (in Weeks) is defined as: (date of the last dose – the date of the first dose + 1)/7.

- Number of doses: Total number of non-zero doses administered during study.
- Cumulative dose (in mg) is defined as the cumulative amount of study drug administered during the treatment period.
- Number of missed doses is defined as: Total number of completely missed doses across study dosing period.

A by-participant listing of exposure to study drug will be generated for the FAS. The listing will include participant identifier, age, gestational age at each visit, treatment status (drug given [Yes, No]), planned dose, dose administered, anatomical location, laterality, route, dose form and date and time of administration.

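### SAP 4.3.4, the neonatal summaries and the exposure listing use eligibility-restricted sets, so an exposed but ineligible pregnancy drops out of those outputs, and SAP 4.8 does not declare the move

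*SAP*

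**What the plan says.** SAP section 3, Table 1 defines the FAS as "All participants that fulfill the criteria for screening part 1 and part 2, and received one or more full doses of RLYB212" and the NFAS as "Neonates born to participants that fulfill the criteria for screening part 1 and part 2 and received one or more doses of RLYB212". The Safety Analysis Set in the same table asks only for any dose, and the one in Protocol 9.3 asks for one or more doses. Neither has an eligibility condition.

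The SAP then assigns sets as follows:

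- Pregnancy outcomes (4.3.4): "percentage with 95% Clopper-Pearson exact confidence interval for the FAS".
- Exposure (4.5.1): the summary is on the Safety Analysis Set, but "A by-participant listing of exposure to study drug will be generated for the FAS".
- Neonatal AEs (4.3.2.1): "The following summaries of neonates will be provided for NFAS". Newborn findings (4.3.2.2), neonatal vital signs (4.3.2.3) and infant health (4.3.5) also use the NFAS.
- Analysis-set accounting (4.1.4.3): "reasons for exclusions from each analysis set will be summarized for FAS".

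Protocol 9.4.5 says "All routine safety analyses will be performed on the Safety Analysis Set" and adds that maternal and neonate/infant data are shown separately. Protocol 8.1.2 provides that, if the fetal genotype is still outstanding at GW 16, "the subject will be dosed with the initial dose of RLYB212 pending the result".

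**The concern.** A safety objective has to describe the pregnancies that were exposed. A set conditioned on eligibility can leave some of them out, and here the protocol itself creates the route: a woman can be dosed while the fetal genotype is pending. If the fetus proves HPA-1b/b, she fails Screening Part 1 inclusion criterion 3d and falls outside the FAS, and her neonate falls outside the NFAS. The same happens to a dosed woman later found to have failed any other criterion. A woman who received only a partial dose is outside the FAS as well.

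The SAP also pulls against itself. Section 4.8 widens the Safety Analysis Set so that any amount of drug counts, while the FAS asks for a full dose. Exposure is summarised on one set and listed on another. Because exclusions are accounted for within the FAS, a woman left out of the FAS is not shown as left out. Section 4.8 announces the FAS and NFAS, but a reader could not tell from it that pregnancy outcomes and neonatal safety had been moved to them.

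**Working it through.** The plan has no figure of its own to reproduce: the sample size of 8 is justified qualitatively and the study is descriptive. The check is a comparison of set assignments, followed by an illustration.

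**1. Which outputs lose an exposed but ineligible pregnancy**

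| Output | SAP section | Set | Pregnancy kept? |
|---|---|---|---|
| Pregnancy outcomes | 4.3.4 | FAS | No |
| Exposure listing | 4.5.1 | FAS | No |
| Neonatal AE summaries | 4.3.2.1 | NFAS | No |
| Newborn findings, neonatal vital signs, infant health | 4.3.2.2, 4.3.2.3, 4.3.5 | NFAS | No |
| Maternal AEs and the named maternal and fetal AE terms | 4.2.2.1 | Safety | Yes |
| Maternal examination, vital signs, laboratory, ECG, ultrasound | 4.2.2.2 to 4.2.2.6 | Safety | Yes |
| Exposure summary | 4.5.1 | Safety | Yes |
| Neonatal AE listing | 4.3.2.1 | none named | Yes |
| Neonatal thrombocytopenia | 4.3.6 | all newborns | Yes |

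**2. How often this could happen in the trial as designed**

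Protocol Table 2-1 gives a chance of roughly 15% that the fetus is HPA-1b/b when a woman is dosed before the genotype is settled. Let f be the share of women dosed at that stage. The documents do not give f, so I assume 0.25, 0.5 and 1. Treating women as independent, among 8 dosed:

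- Expected number = 8 × 0.15 × f
- Chance of at least one = 1 − (1 − 0.15 f)^8

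| f | Expected number | Chance of at least one |
|---|---|---|
| 0.25 | 0.3 | 1 − 0.9625^8 = 26% |
| 0.5 | 0.6 | 1 − 0.925^8 = 46% |
| 1 | 1.2 | 1 − 0.85^8 = 73% |

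**3. What one omitted event does to the pregnancy-outcome table**

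Suppose 9 women are dosed: 8 eligible without a fetal loss, and 1 dosed with the genotype pending whose fetus is HPA-1b/b and who has a loss. The exact Clopper-Pearson 95% intervals are:

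- FAS: 0/8 = 0%. Upper limit 1 − 0.025^(1/8) = 36.9%, so 0 to 36.9%.
- All dosed women: 1/9 = 11.1%. Lower limit 1 − 0.975^(1/9) = 0.3%. Upper limit is the 0.975 quantile of Beta(2, 8) = 48.2%.

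**4. Whether her outcome would be in the database**

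Protocol 7.1 keeps a woman who stops treatment in the study for pregnancy outcome and postnatal follow-up. Protocol 8.1.2 discharges her after a safety visit 4 weeks later, and the synopsis also discharges her. Even under 8.1.2, a dose at GW 16 leads to a visit at GW 20, which is past the GW 19 boundary between spontaneous abortion and stillbirth in Protocol 9.4.3. A loss in that window could be recorded. Later outcomes depend on which passage governs.

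**5. What is left after SAP 4.9**

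Section 4.9 reports one participant enrolled, cancels all tables and figures, and keeps participant-level listings. It does not restate the sets for those listings. The FAS percentage and interval in 4.3.4 and the exclusion summary are no longer produced. The FAS label on the exposure listing and the NFAS label on the newborn and infant listings remain.

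**The case against.** A reader might infer that exposed pregnancies failing a criterion disappear from the safety reporting altogether. The documents do not support that. As the table shows, most maternal and fetal safety outputs stay on the Safety Analysis Set, the neonatal AE listing names no set, and thrombocytopenia covers all newborns. A reader might also take the major-deviation listing to be restricted. SAP 4.1.4.2 names no set for that listing; only its summary uses the FAS.

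The other objections, and what stands of each:

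- **The protocol names no set for pregnancy outcomes.** Correct. They sit in 9.4.3, and the outputs enumerated in 9.4.5 do not include them. The departure rests on reading 9.4.5 together with 9.4.2, which points to 9.4.3 as the safety assessment. For neonatal safety data the link to 9.4.5 is direct.
- **The secondary objective concerns the HPA-1a positive neonate.** This justifies a labelled subset. It does not justify the NFAS filter, which would also drop an HPA-1a positive neonate whose mother failed some other criterion.
- **Dosing with the genotype pending does not itself exclude a woman.** Correct. The FAS does not say the criteria must be met at the time of dosing, and in roughly 85% of such cases the result would be HPA-1a/b.
- **With an HPA-1b/b fetus there may be no later data to include.** This stands if 8.1.2 and the synopsis govern, except for events up to the safety visit. It does not stand if 7.1 governs.
- **The affected tables are cancelled.** Correct. This largely removes the practical effect.

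**Conclusion.** The concern holds in a limited form. Pregnancy outcomes, the neonatal summaries listed above and the exposure listing are on sets conditioned on eligibility (and on a full dose for the FAS). This departs from Protocol 9.4.5, directly for neonatal safety and by cross-reference for pregnancy outcomes, and SAP 4.8 does not declare it.

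For the trial as designed, the contrast is 0/8 (0 to 36.9%) against 1/9 (0.3 to 48.2%) if one excluded pregnancy has an event. The chance of at least one HPA-1b/b pregnancy among 8 dosed women is 26% to 73%. That range rests on the protocol's 15%, on independence and on an assumed f of 0.25 to 1.

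For the trial as it ended, with one participant and listings only, the contrast cannot arise. What remains is an ambiguity about which set governs the exposure and newborn/infant listings. With one participant, inclusion in each is all or nothing.

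**What to change.** - Use the Safety Analysis Set for SAP 4.3.4 and for the exposure listing in 4.5.1.
- For 4.3.2 and 4.3.5, define the neonatal set as all neonates born to women in the Safety Analysis Set. Carry an eligibility and genotype flag, and show HPA-1a positive neonates as a labelled subset.
- In 4.1.4.3, account for analysis-set exclusions over all dosed women.
- In 4.8, record any output deliberately kept on a set other than the one Protocol 9.4.5 names.
- In 4.9, state that the listings cover all dosed women and their neonates.
- Reconcile Protocol 7.1 with 8.1.2 and the synopsis on follow-up of a woman whose fetus is HPA-1b/b, because those passages decide whether her outcome data exist.

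Sections 4.3.6 and the major-deviation listing need no change. On the SAP side the cost is wording and a filter. The downside is that a few off-target pregnancies would appear and have to be read with the flag.

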4.3.6. Neonatal Thrombocytopenia

A cord blood sample will be collected at delivery to assess the possible occurrence of neonatal thrombocytopenia and severe neonatal thrombocytopenia, as determined by a cord blood platelet count $< 150 \times 10^9/L$ and $< 50 \times 10^9/L$ respectively.

All available data will be summarized and listed for all newborns. The incidence of Neonatal thrombocytopenia and severe neonatal thrombocytopenia will also be summarized by frequency and percentage with 95% Clopper-Pearson exact confidence interval.

4.3.7. Post Pregnancy HPA-1a Alloimmunization

Serum samples will be tested at the Week 10 postpartum timepoint to assess for the occurrence of HPA-1a alloimmunization during the pregnancy and early postpartum period.

The presence of post pregnancy maternal anti-HPA-1a alloantibodies will be summarized by frequency and percentage with 95% Clopper-Pearson exact confidence interval for AAS.

4.3.8. Sensitivity Analysis

Not Applicable

4.3.9. Supplementary Analyses

Not Applicable

4.4. Exploratory Endpoint Analysis

Not applicable

4.5. Other Analyses

4.5.1. Extent of Exposure

Study drug exposure will be summarized for participants who received RLYB212 for the safety analysis set, for duration of exposure, number of doses, cumulative dose, and number of missed doses.

Duration of exposure (in Weeks) is defined as: (date of the last dose – the date of the first dose + 1)/7.

- Number of doses: Total number of non-zero doses administered during study.
- Cumulative dose (in mg) is defined as the cumulative amount of study drug administered during the treatment period.
- Number of missed doses is defined as: Total number of completely missed doses across study dosing period.

A by-participant listing of exposure to study drug will be generated for the FAS. The listing will include participant identifier, age, gestational age at each visit, treatment status (drug given [Yes, No]), planned dose, dose administered, anatomical location, laterality, route, dose form and date and time of administration.

